12.1 Submission of data

Electronic CRFs: following each participant visit the designated site staff will complete the visit specific eCRF. Once all required information is received the eCRF shall be considered complete. Project Team staff

will then monitor the data for completeness and accuracy. Any eCRF discrepancies, either manual or automatic, will be addressed with the site staff for clarification.

The site Principal Investigator is responsible for ensuring the completion of accurate source documentation to support data collected on case report forms. Source documents include all recordings of observations or notations of clinical activities and all reports and records necessary for the evaluation and reconstruction of the trial. Source documents include, but are not limited to; participant medical records, laboratory reports, ECG tracings, X-rays, radiologist reports, participant diaries, biopsy reports, ultrasound images, participant progress notes, pharmacy records and any other reports or records of procedures performed in accordance with the protocol.

It is not acceptable for the CRF to be the only record of study participation and progress must also be recorded in the each person's medical record. This is to ensure that anyone accessing the medical record has adequate knowledge that the person is a clinical trial participant.

Any document that acts as a source document (the point of the initial recording of a piece of data) should be signed and dated by the person recording or reviewing the data for issues of medical significance (for example the review of laboratory reports). Persons signing the source documents must be listed as a site staff member.

The sponsor's monitor will visit sites to conduct source document verification. The number of visits will depend upon study complexity and recruitment rate; however, the monitor will conduct a minimum of two source data verification visits during the study. These should occur shortly after randomization of the first participant(s) and following completion of all study visits.

The Principal Investigator is responsible for retaining all essential documents listed in ICH Good Clinical Practice guidelines. These must be organised in a comprehensive filing system that is accessible to study monitors and other relevant personnel.

12.2 Linkage of data

Study data will be periodically linked with public registries, for example the National Notifiable Diseases Database, hospital morbidity databases, cancer and death registries. Ethics approval from the Population Health Ethics Committee, and all other required Human Research Ethics Committees will be obtained prior to any linkage study being performed.

12.3 Retention of Data Linkage Records

All datasets relating to the project will be held at CHeRel and AIHW for at least 12 months following the last update so that the linkage can be recreated should a problem with the linkage be identified at the

time of analysis. The electronic data files will be retained by the Kirby Institute for 7 years after the publication of the study results. At the end of this period, the Kirby Institute Information Technology staff will follow standard operating procedures to delete the archived electronic records.

12.4 Archiving

The Principal Investigator is responsible for ensuring all study documents are retained for a minimum of 15 years following completion and publication of the study.

13. Ethics committee/regulatory approval and informed consent

The sponsor is responsible for ensuring regulatory approval for the study is obtained where required.

The site Principal Investigator is responsible for obtaining IRB/EC approval for the protocol and participant information and informed consent form in compliance with local regulatory requirements prior to entering any participant into the study. The approval letter/document must clearly identify the protocol and all documents approved by the IRB/IEC including version number & date of the protocol and participant information and consent form. A copy of the approval document must be sent to the study sponsor.

The site Principal Investigator must also obtain approval for any amendments to the protocol or participant information and informed consent form. The Principal Investigator must comply with all IRB/IEC reporting requirements for all adverse events, annual updates and end of study reports and must agree to abide by any IRB/IEC conditions of approval.

The site Principal Investigator (or designee) is responsible for ensuring freely-given consent is obtained from each potential participant prior to the conduct of any protocol-specific procedures. The Principal Investigator may delegate the task of obtaining consent to appropriately qualified Sub-investigator(s). Consent must be documented by the participant's dated signature on the participant information and consent form together with the dated signature of the person conducting the consent discussion.

If the participant is illiterate, an impartial witness should be present during the entire consent discussion. Once the discussion is complete, the participant must sign and date the informed consent form, if capable. The impartial witness must also sign and date the consent form along with the person who conducted the consent discussion.

If the participant is legally incompetent (i.e. under 18 years of age or mentally incapacitated) the written consent of a parent, guardian or legally authorised representative must be obtained.

A copy of the signed and dated participant information and consent form must be given to the person prior to study participation. The participant or their legally authorised representative must be informed in a timely manner of any new information that becomes available during the course of the study that may affect his/her willingness to continue study participation.

This study shall be conducted in accordance with the ethical principles laid out in the Declaration of Helsinki (most current issued version) and the National Statement on Ethical Conduct in Research Involving Humans (most current issued version).

14. Confidentiality of data

14.1 Confidentiality of participant records

By signing the Clinical Trial Agreement, the site Principal Investigator agrees that the sponsor, IRB/IEC or regulatory authorities may consult and/or copy study documents to verify information in the case report form. By signing the consent form the participant agrees to these processes. The following wording may be included in the protocol.

Participant confidentiality will be maintained at all times and no documents containing the participant's name or other identifying information will be collected by the sponsor. It may be necessary for the sponsor's representatives, the IRB/IEC and regulatory authority representatives to have direct access to the participant's medical records. If study documents need to be photocopied during the process of verifying case report form data, the participant will be identified by a unique code only; full names and other identifying information will be masked.

Confidentiality of Personal Information for Data Linkage

The Kirby Institute has a strict participant data confidentiality policy. An independent Data Custodian will be appointed for this study to manage the identifiable data required for data linkage. The Data Custodian will not be involved in the conduct of the study, and in most cases, will be a Data Manager. The role of the Data Custodian is to ensure that identifiable information is collected, used, accessed, stored and destroyed in line with HREC approval and in accordance with the participant data confidentiality policy and the NHMRC National Statement on Ethical Conduct in Research Involving Humans (2007). The Data Custodian will be responsible for the exchange of information with data linkage services, and for provision of de-identified linked records back to the person/s who requested the data linkage. Once the linked data file is received by the Data Custodian at the Kirby Institute, all study data will be transferred to a secure network protected by a firewall and individual files will also be password-protected. All results will be published in a form that will not allow individuals to be identified, that is, in tabular, aggregate form only; no individual results will be disclosed.

14.2 Confidentiality of study data

By signing the Clinical Trial Agreement, the site Principal Investigator affirms to the sponsor that information provided to them by the sponsor will be maintained in confidence and divulged only as necessary to the ethics committee and institution employees directly involved in the study. Both ethics committee members and employees must also understand the confidentiality requirements for any information divulged to them. The data generated by this study will be considered confidential, except where it is included in a publication as agreed in the publication policy of this protocol.

15. Governance

The study is sponsored by UNSW and coordinated through the Kirby Institute. It is funded by the University of New South Wales (UNSW) and Merck Sharpe and Dohme. The Kirby Institute has established governance and implementation structures which use resources efficiently to deliver program objectives on schedule.

16. Quality Control (QC) and Quality Assurance (QA)

The sponsor agrees to be responsible for implementing and maintaining quality control and quality assurance systems with written standard operating procedures to ensure the study is conducted and data are generated, documented and reported in compliance with the protocol, Good Clinical Practice standards and all applicable local laws and regulations relating to the conduct of a clinical trial.

17. Publication Policy

The results of this study may be published and presented at scientific meetings. Publication of data derived from this protocol will be governed by the Protocol Steering Committee. All published data will be non-identifiable grouped data.

18. List of References

1. Nelson, P.K. et al. Global epidemiology of hepatitis B and hepatitis C in people who inject drugs: results of systematic reviews. *Lancet* **378**, 571-83 (2011).
3. Seeff, L.B. The history of the "natural history" of hepatitis C (1968-2009). *Liver Int* **29 Suppl 1**, 89-99 (2009).

32. Aspinall, E.J. et al. Treatment of hepatitis C virus infection among people who are actively injecting drugs: a systematic review and meta-analysis. *Clin Infect Dis* **57 Suppl 2**, S80-9 (2013).

19. Abbreviations List

ALT	Alanine Aminotransferase
AST	Aspartate Aminotransferase
DAA	Direct Acting Antiviral
End of treatment	Date of last dose of treatment
ETR	End of Treatment Response, undetectable HCV RNA at the completion of treatment
FBC	Full Blood Count (haemoglobin, WCC including differentials, platelets)
HCV	Hepatitis C Virus
IDUs	Injection Drug Users
IEC	Institutional Ethics Committee (Human Research Ethics Committee)
INR	International Normalized Ratio
IRB	Institutional Review Board (Human Research Ethics Committee)
LFTs	Liver Function Tests – albumin, ALT, AST, alkaline phosphatase, GGT, total bilirubin, total protein
LLOQ	Lower Limit Of Quantification
GGT	Gamma Glutamic Transpeptidase
Hgb	Haemoglobin
OST	Opioid Substitution Therapy
PEG-IFN	Pegylated interferon alfa 2a
PWID	People Who Inject Drugs
POC	Point of Care
RAS	Resistant Associated Substitutions
Reinfection	Detection of infection with an HCV strain which was distinct from the primary infecting strain among participants with either spontaneous or treatment-induced HCV virological suppression (≤ 15 IU/ml on Roche TaqMan).
SVR12	Sustained Virological Response, HCV RNA undetectable 12 weeks post-treatment
SVR24	Sustained Virological Response, HCV RNA undetectable 24 weeks post-treatment
Undetectable HCV RNA	HCV RNA results that are < 15 IU/ml (non-quantifiable), but “detectable” will be considered as undetectable HCV RNA
WCC	White Cell Count

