9.1 Laboratory supplies and sample processing

Laboratory supplies for collection of research specimens (plasma and whole blood) will be supplied by the Kirby Institute.

The following blood samples will be collected as time point specified in the schedule of assessments:

1. 10 mL EDTA plasma for HCV RNA testing and future HCV related research (20 mL will be collected at Screening and Baseline visits);
2. 4mL whole blood for human genomic DNA analysis collected at the screening and baseline visits only.

Samples will be collected by sites and then processed and stored at -70°C at the site local laboratory for bulk shipment to the Kirby Institute laboratory. Detailed sample processing instructions will be provided in the laboratory manual.

EDTA plasma samples will be used for study endpoint analysis. HCV viral load will be measured using in-house and commercial assays. Sequencing of the viral genome will also be performed as a more accurate means of genotyping. Data generated from the sequencing may also be used to distinguish relapse from reinfection and to examine the prevalence of mixed infection.

HCV sequencing/resistance testing

Sanger sequencing will be performed on a pre-treatment sample on all participants. Complementary RNA will be generated using SuperScript® VILO™ cDNA Synthesis Kit (Life Technologies, Carlsbad, CA) with random hexamers. Sequencing of NS5A will be performed on all participants. A fragment of the HCV genome covering Core, Envelope-1, hypervariable region-1 and beginning of Envelope-2 (E2) will be amplified using a method previously described. Sequencing of NS3/4, NS5A, NS5B, and full-length next generation sequencing may also be performed. Purified amplicons will be sequenced using the Sanger method and sequence chromatograms processed using RECall: a fully automated sequence analysis pipeline. Subtypes will be determined using the Oxford HCV Automated Subtype Tool. Reverse transcription, PCR and sequencing reaction and thermal cycling conditions will be performed as previously described. Further, Sanger sequencing and next generation sequencing will be performed among samples with persistent infection at risk of HCV mixed infection (e.g. treatment non-response). Lastly, Sanger sequencing and next generation sequencing will be performed among samples with HCV recurrence to distinguish HCV reinfection from viral relapse (detectable HCV RNA following HCV virological suppression).

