All participants with an ETR will be followed for up to three years post-ETR to assess HCV reinfection. Participants with viral recurrence (detectable HCV RNA following HCV virological suppression, reinfection rate: 8/100 person years, estimated n=27 x 2 samples=54 total samples) will be identified and available follow-up plasma samples assessed for re-infection.

The sensitivity and specificity of the Xpert® HCV Viral Load point-of-care test for detection of HCV RNA in plasma samples collected via venepuncture and capillary whole-blood samples collected by finger-stick will be assessed using both detectable and quantifiable thresholds (limit of quantification >10 IU/mL) for each assay compared to the local laboratory HCV RNA assay in plasma as the gold standard. A Bland-Altman difference plot will be generated to assess bias and agreement measurements, including limits of agreement, between the quantification of HCV by Xpert® HCV Viral Load both sample types, compared to the local laboratory HCV RNA assay in plasma.

11. Data Safety and Monitoring Board (DSMB).

A Data Safety Monitoring Board will not be used for this study as the drug is being prescribed and supplied according to indication via the PBS.

The study Medical Monitor, A/[name] will oversee all serious adverse events for DARLO-C. A/[name] is independent of the study project management team and Protocol Steering Committee. A/[name] is also a clinician at St Vincent's Hospital which is one of the recruiting sites. Should an SAE occur in a patient under A/[name] care the project team will seek an independent review of the SAE from a suitably qualified independent Infectious Diseases Specialist or Hepatologist.

12. Data collection, source documents and record retention

The Principal Investigator and the institution where the study will be conducted will permit study-related monitoring, audits, ethics committee review and regulatory inspection providing direct access to source documents.

Data will be collected on study specific electronic or paper copy case record forms. The Principal Investigator is responsible for ensuring the data collected are complete, accurate and recorded in a timely manner.

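### The reinfection definition compares recurrent virus with one pre-treatment strain, has no rule for a minority strain already present, and does not clearly require deep sequencing of the paired pre-treatment sample

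*Combined protocol and SAP*

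**What the plan says.** - **Definition.** The Reinfection entry in Section 19 (Abbreviations List) reads "Detection of infection with an HCV strain which was distinct from the primary infecting strain", among participants whose virus has been suppressed. It names no sequencing method and does not mention mixed infection.
- **Pre-treatment sequencing.** Section 9.1: "Sanger sequencing will be performed on a pre-treatment sample on all participants". Beyond that, "Sequencing of NS3/4, NS5A, NS5B, and full-length next generation sequencing may also be performed", which is permission and not a requirement. Section 10 (Evaluation of HCV phylogenetics) also has all available screening or baseline samples sequenced, without naming a method.
- **Sequencing at recurrence.** Section 9.1: "Sanger sequencing and next generation sequencing will be performed among samples with HCV recurrence to distinguish HCV reinfection from viral relapse".
- **Mixed infection.** Section 9.1: "Sanger sequencing and next generation sequencing will be performed among samples with persistent infection at risk of HCV mixed infection", with non-response as its example. It adds: "Data generated from the sequencing may also be used to distinguish relapse from reinfection and to examine the prevalence of mixed infection".
- **Number of samples.** Section 10 (Evaluation of HCV re-infection) gives "estimated n=27 x 2 samples=54 total samples". It refers to follow-up plasma where available and does not say which two time points make up the pair.
- **Endpoint and sizing.** Section 10 starts time at risk at undetectable RNA at end of treatment. It plans a Poisson confidence interval and a Cox model, states the hypothesis of a rate below 8 per 100 person-years, and expects 27 reinfections in 337 person-years.

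**The concern.** Calling a recurrence a reinfection means saying that the strain arrived after treatment. That requires knowing what was there before. A Sanger read gives one consensus sequence per amplified fragment and so mainly reflects the dominant strain. The plan seems to accept this limit, since it adds NGS wherever mixed infection is the question.

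NGS of the recurrence sample shows what is present then. It cannot show that the strain was absent at baseline. If the pre-treatment comparator is a consensus sequence, a minority strain missed at baseline looks new when it re-emerges, and the definition as worded makes it a reinfection.

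Two things are at stake. The incidence rate, which is the secondary endpoint, would be biased upward. The Cox model would also take in events that did not arise from exposure after treatment. If those events are unrelated to injecting behaviour, they pull the hazard ratios of Hypothesis 2.2 towards 1.

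**Working it through.** **Inputs (Section 10).** 27 reinfections; 337 person-years; hazard ratio 2.94; alpha 0.05 (taken as two-sided); covariate 50% prevalent; hypothesis of a rate below 8 per 100 person-years.

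**Step 1: reproduce the plan's figures.**
- Rate: 27/337 = 8.01 per 100 person-years. This agrees with the stated 8.
- 95% interval: exact Poisson gives 5.28 to 11.66, against a stated 5.3 to 11.4. An exact binomial interval on 27/337 gives 5.35 to 11.44, which is closer. The difference does not bear on this point.
- Power (Schoenfeld): √(27 × 0.25) × ln 2.94 − 1.96 = 2.598 × 1.078 − 1.96 = 0.842, so power is 80.0%. This agrees with the stated 80%.

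**Step 2: effect of one case.** 1/337 = 0.30 per 100 person-years. With 26 events the rate is 26/337 = 7.72.

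**Step 3: range.** Let k be the number of the 27 events that are really pre-existing minority strains. The documents give no prevalence of mixed infection, so k is an assumption. Person-years stay at 337, which corresponds to censoring these participants at their estimated recurrence date. Rate = (27 − k)/337, with exact Poisson limits and Schoenfeld power at hazard ratio 2.94.

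| k | True reinfections | Rate per 100 p-yrs (95% CI) | Overstatement | Power |
|---|---|---|---|---|
| 0 | 27 | 8.01 (5.28 to 11.66) | 0 | 80.0% |
| 1 | 26 | 7.72 (5.04 to 11.30) | 0.30 | 78.5% |
| 2 | 25 | 7.42 (4.80 to 10.95) | 0.59 | 76.9% |
| 3 | 24 | 7.12 (4.56 to 10.60) | 0.89 | 75.2% |
| 5 | 22 | 6.53 (4.09 to 9.88) | 1.48 | 71.5% |

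**Step 4: effect on the hypothesis.** At the planning value, one case moves the point estimate across 8. The upper limit stays above 8 for every k shown. It falls below 8 only at 16 events or fewer (16/337 = 4.75, upper limit 7.71), that is, if 27 − 16 = 11 events were reclassified.

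**The case against.** The case for the plan has four parts.

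- **NGS is promised for this distinction.** Section 9.1 commits to Sanger and NGS at recurrence in order to separate reinfection from relapse, and any such comparison needs a pre-treatment comparator. A reader might infer that Sanger is the only method used, or that counting re-emergent strains as reinfection is a stated rule. Neither is in the documents. Misclassification is a possible result of following the definition literally.
- **The 54 samples may already be pairs.** Two samples per recurrence fits one pre-treatment and one recurrence sample. It fits two follow-up samples equally well, and the sentence mentions only follow-up plasma. This stands as an ambiguity. It also means that the 54 cannot be cited as proof that the fix is free.
- **Most surviving strains would be caught elsewhere.** A strain that treatment does not suppress should show as detectable RNA at Week 4 or end of treatment, and non-response is already directed to a mixed-infection work-up. This narrows the problem to strains suppressed at end of treatment that rebound later. That group is not empty by design: time at risk starts at end of treatment and not at SVR12, and Section 19 treats detectable RNA below 15 IU/mL as undetectable.
- **The size is unknown.** A reader might infer that a minority strain of a genotype other than 1 or 4 is especially likely to survive, or might multiply an assumed prevalence by an assumed emergence fraction to get a share of false events. The documents give no activity by genotype, no prevalence and no emergence fraction, so they support neither step.

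**Conclusion.** The gap is real and limited. The definition has one reference strain and no rule for a minority strain present before treatment, and NGS of the paired pre-treatment sample is not clearly required. Followed literally, such a strain re-emerging after suppression is a reinfection event.

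The bias is upward, at about 0.30 per 100 person-years per case. For an assumed 1 to 5 cases it is 0.3 to 1.5 per 100 person-years. This rests on the plan's 27 events and 337 person-years and on an illustrative range, not on an estimate of how common such cases are.

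A reader might infer that a single event decides the below-8 hypothesis. That is true only of the point estimate, and only because the planning rate sits on the threshold. Section 10 states no decision rule on the point estimate, and the upper limit exceeds 8 across the range. SVR12 is not affected, because it depends on undetectable RNA and not on strain.

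This is a worthwhile, inexpensive improvement to a secondary endpoint and does not undermine the design.

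**What to change.** 1. In Section 19, define reinfection as infection with a strain distinct from all strains detected before treatment.
2. In Sections 9.1 and 10, state that the two samples per recurrence are the stored Screening or Baseline sample and the recurrence sample, and that both undergo NGS.
3. Classify a match to a pre-treatment minority strain as persistence of a pre-existing (mixed) infection and not as reinfection. Report these cases separately, and state that their time at risk is censored at the estimated recurrence date.
4. State how a recurrence is classified when its pre-treatment sample cannot be deep-sequenced.
5. Give the incidence rate and the Cox model with and without the matched cases, as a sensitivity analysis.

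**Cost.** No new visit or sample is needed: Section 9.1 already has 20 mL EDTA collected at Screening and at Baseline and stored at −70°C. If the pairs are not already budgeted, the change adds up to about 27 sequencing runs, one pre-treatment sample per expected recurrence. The Cox model may have slightly fewer events (26 give 78.5% instead of 80.0% power at hazard ratio 2.94), but the events removed would not have been reinfections.
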